## **6.2 HANDLING OF MISSING AND INCOMPLETE DATA**

Attempt will be made to ensure that patients come back for scheduled follow-up evaluations. In case of missing data, for clinical outcome scores, Last Observation Carried Forward will be used to impute the missing data. For survivorship analysis, the data including implant in situ collected in the next follow-up will be used to calculate survivorship

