### 1.4. PURPOSES

A PROSPECTIVE SINGLE-CENTER STUDY ON E1 ACETABULAR LINER IN THA

The purpose of the study is to evaluate clinical performance of E1 liner in THA in Korean patient population.. The clinical performance will be evaluated based on patient outcomes, radiographic assessment and survivorship.

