### 2.4. PRIMARY AND SECONDARY ENDPOINTS

Primary endpoint is HHS score at 1 year follow-up.

Secondary endpoints include

- HHS at other follow-up visits
- EQ5D, UCLA at 6month, 1 year, 2 year, 5 year postop
- Radiographic Assessment at Immediate post-op, 6 months, 1 year, 2 year, 5 year postop
- Survivorship up to 10 years

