**2.5.2. ASEESMENT TIMELINES/SCHEDULE**

Clinical and Radiographic Exams									
Data Collection item	Pre-operative	Intra-operative	Immediate Post-operative	6 Months	1 Year	2years	5 years	7 years	10 years
Demographic and Medical History	X								
Operative Record		X							
Clinical Evaluation – HHS, EQ5D, UCLA	X			X	X	X	X		
Radiographic assessment			X	X	X	X	X		X
Wear Analysis				X	X	X	X		X
Phone Interview								X	
Adverse events including revisions	As required								

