### 3.3. SUBJECT WITHDRAWAL

It is recognized that the subject's participation in this trial is entirely voluntary, and that she/he may refuse to participate and may withdraw from participation at any time without jeopardy to any future medical care. It is also recognized that the investigator, at his/her discretion, may withdraw a subject from this study based upon his/her professional judgment. In event of subject withdrawal, applicable local procedures should be followed

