## 6. STATISTICAL ANALYSIS PLAN

### 6.1 SAMPLE SIZE CALCULATION

The primary objective of this study is to show that there is a significant increase in Harris Hip Scores from baseline to 1 year post-surgery. The hypothesis can be stated as follows:

$$H_0: \mu_d = 0 \quad \text{vs.} \quad H_A: \mu_d \neq 0,$$

Where  $\mu_d$  = the mean of the paired differences ( $HHS_{1\text{Year}} - HHS_{\text{preop}}$ ).

This hypothesis will be tested using a paired t-test of mean difference equal to zero.

Harris Hip Score difference of **4 points** was shown to be the best cutoff point for optimal sensitivity and specificity to detect clinical improvement (Hoeskma et al. Ann Rheum Dis 2003; 62: 935–938).

If we choose to detect a least clinical acceptable difference in Harris Hip Score of **5 points** with the following assumptions:

$\alpha = 0.05$	Probability of Type I Error
$\beta = 0.10$	Probability of Type II Error
$s_d = 15.16$	Estimated standard deviation of the differences (based on Biomet previous Arcom and ArcomXL study)

Sample size required is N= 99 rounds to 100 subjects.

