## **6.3 DATA ANALYSES**

The following analyses will be performed:

1. Primary Endpoint – mean HHS score at 1 year
2. Second Endpoints – mean HHS score at other postop time points
3. Other Clinical Outcomes scores including EQ5D and UCLA
4. Comparison in clinical outcomes scores between preoperative and various postoperative time points
5. Survivorship with endpoint being revisions.

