### **8. DATA REPORTING**

#### **8.1 INTERIM REPORT**

An interim report will be provided after each follow-up period.

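### Last observation carried forward is the only rule for missing HHS, EQ5D and UCLA scores; read plainly, it enters pre-operative scores as post-operative results and biases the reported means

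*Combined protocol and SAP*

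**What the plan says.** - **Missing scores (6.2):** "In case of missing data, for clinical outcome scores, Last Observation Carried Forward will be used to impute the missing data". The section's only other rule concerns survivorship. It states no missingness assumption, no limit on how far a score may be carried, and no exception when the last value is pre-operative.
- **Schedule (2.5.2):** the row "Clinical Evaluation – HHS, EQ5D, UCLA" is marked pre-operatively and at 6 months, 1, 2 and 5 years. Section 2.4 agrees for the secondary scores: "EQ5D, UCLA at 6month, 1 year, 2 year, 5 year postop".
- **Primary test (6.1), on the 1-year minus pre-operative HHS difference:** "This hypothesis will be tested using a paired t-test of mean difference equal to zero".
- **Analyses (6.3):** mean HHS at 1 year as the primary summary, mean HHS at the other visits, the other scores, and "Comparison in clinical outcomes scores between preoperative and various postoperative time points". No sensitivity analysis is listed.
- **Use of the results:** section 1.4 says "The clinical performance will be evaluated based on patient outcomes, radiographic assessment and survivorship", and section 8.1 says "An interim report will be provided after each follow-up period".
- **Withdrawal (3.3):** subjects "may withdraw from participation at any time", so early loss of all post-operative scores is possible.

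**The concern.** LOCF is harmless only if a score would not have changed since it was last measured. Surgery is meant to change these scores, and the only measurement before 6 months is taken before surgery. A pre-operative value carried forward therefore assigns the patient no benefit, by construction.

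This is a single-arm study, so no comparison group exists in which such an error could cancel. The means at each visit are themselves the result, and they go into a report after every follow-up period. At 2 and 5 years the rule has a different effect: it holds a patient at the last attended visit, so any later decline is hidden and any later improvement is missed.

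**Working it through.** **Inputs.** From 6.1: SD of paired differences 15.16, design difference 5 points, alpha 0.05 two-sided, beta 0.10, N = 99 rounded to 100. The documents give no missing rate, no expected gain and no later course of scores. Values for these below are assumptions.

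**1. The plan's own figure.** A paired t-test with these inputs (noncentral t) needs N = 99, with power 90.1%, or 90.4% at 100. The normal approximation gives (15.16 × (1.960 + 1.282) / 5)² = 96.6, so 97. The stated N is reproduced and is not in dispute.

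**2. What LOCF puts in each cell** (reading 6.2 with 2.5.2, for a patient who has a pre-operative score):

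| Missed score | Value filled in |
|---|---|
| 6 months | pre-operative |
| 1 year, 6 months observed | 6-month score |
| 1 year, 6 months also missed | pre-operative; paired difference exactly 0 |
| 2 or 5 years | last post-operative score, or pre-operative if there is none |

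**3. Pre-operative score carried.** If a share f is filled this way and those patients' true mean gain is G_m, the bias in the mean change is -f × G_m. With G_m equal to the overall gain:

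| f | gain 5 (design difference) | gain 20 (assumed) |
|---|---|---|
| 5% | -0.25 | -1.0 |
| 10% | -0.5 | -2.0 |
| 20% | -1.0 | -4.0 |

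At 6 months, f is the share missing that visit. At 1 year it is only the share missing both visits.

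**4. The 1-year mean overall.** Let g be the share missing 1 year, h the share of those who also miss 6 months, and r the 6-month gain as a fraction of the 1-year gain μ. The bias is -g × [hμ + (1 - h)(1 - r)μ]. With g = 10-20%, h = 25-100% and r = 0.8-1.0, it runs from about -0.1 to -1.0 at μ = 5 and from -0.5 to -4.0 at μ = 20. Carrying a 6-month score alone does little harm: with 10% carried and a further gain of 2 or 5 points, the bias is -0.2 or -0.5.

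**5. The 5-year mean.** The bias is -(share carried) × (true change since the last score). With 10-30% carried:
- a decline of 10 points gives +1.0 to +3.0;
- no change gives 0;
- an improvement of 5 points gives -0.5 to -1.5.

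**6. The primary test, missingness unrelated to scores.** With gain 5 and f = 10%, the LOCF mean is 4.5 and its SD is √(0.9 × 15.16² + 0.09 × 5²) = 14.46. The ratio to the standard error is 4.5 / 1.446 = 3.11. For 90 observed pairs it is 5 / (15.16/√90) = 3.13. Power is 86.9% against 87.2%, and simulated rejection at gain 0 is 0.050.

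**7. The primary test, missingness depending on the pre-operative score.** Assumptions: score SDs 15.16; correlation 0.5 with pre-op and 0.7 between 6 months and 1 year; about 10.5% lose both post-operative scores, more often when the pre-operative score is low. Simulated bias at gains 5 and 20:
- LOCF: -1.15 and -2.72
- observed pairs: -0.70 and -0.70
- repeated-measures model: 0.02 and 0.02

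The LOCF slope is (2.72 - 1.15)/15 = 0.105 per point of gain, so at gain 0 the LOCF bias is about -1.15 + 5 × 0.105 = -0.63. Against a standard error of √0.895 × 15.16/10 = 1.43, that is a shift of 0.44 standard errors. Rejection at gain 0 is then about Φ(-1.52) + Φ(-2.40) = 0.064 + 0.008 = 0.072, matching a simulated 0.073. Nearly all of it is in the direction of worsening. Simulated power at gain 5 is 0.76. Observed pairs gave the same rejection rate and power as LOCF.

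**The case against.** **The plan does not say that a pre-operative score may be carried, and it defines no analysis set.** This is true, so the 0 difference is an inference from the plain wording. It does not rescue the rule: if only post-operative scores may be carried, a missed 6-month score has no rule at all. The text needs repair on either reading.

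**At the plan's own 5-point figure the bias is small.** This also stands. It is 0.25 to 0.5 points for 5-10% carried, and at 1 year those patients must miss both visits despite a window of 3 months either side and the retention effort promised in 6.2. Larger values need larger gains, and at a gain of 20 the finding that HHS improved is not in doubt. The effect is on the reported size of the gain.

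**A reader might infer that LOCF makes the primary test invalid or too liberal.** The documents do not support this. When missingness is unrelated to scores, the test keeps its level and matches observed pairs for power. When it depends on the pre-operative score, level and power do suffer, but equally for observed pairs, so the fault is not specific to LOCF.

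**A reader might also infer that LOCF flatters the device.** That holds only at later visits, and only if scores decline. Carrying the pre-operative score works against the device.

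**A smaller repair might do:** no pre-operative carry-forward, observed numbers reported, and one sensitivity analysis. That would remove the worst feature. It would still leave the late visits frozen and, without a model, would not correct for loss related to earlier scores.

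**Conclusion.** The concern holds as one of bias in the reported means, and it should be fixed. LOCF is the only stated rule, nothing checks it, and on its plain reading it reports pre-operative scores as results of surgery. The bias is -f times the missing patients' true gain wherever the pre-operative score is carried. At 2 and 5 years its sign follows the true course of the scores after the last visit.

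The sizes rest on assumed missing rates and gains. The table values also assume that missing patients gain as much as the others; step 7 shows that the bias is larger when they would have gained more. The plan names no confidence interval, so no claim about interval coverage is made. The documents do not support saying that the primary conclusion would reverse.

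**What to change.** **Section 6.2.** Replace the LOCF sentence with text such as: *Missing clinical scores will not be imputed in the main analysis. HHS, EQ5D and UCLA will each be analysed with a mixed model for repeated measures on all observed scores (pre-operative, 6 months, 1, 2 and 5 years), with visit as a categorical factor and an unstructured covariance, fitted by restricted maximum likelihood. A pre-operative score will never be carried forward as a post-operative score. The number of observed scores will be reported at each visit.* Keep LOCF at most as a sensitivity analysis. State there, too, how scores after revision or death are treated, since 6.2 is silent on this and the model needs the decision.

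**Sections 6.1 and 6.3.** Name the model's 1-year minus pre-operative HHS contrast as the primary test, and report the model mean at 1 year beside it. Otherwise 6.1 would still name the paired t-test and the primary analysis would be stated two ways. With complete data the contrast has the same estimate and standard error as the paired t-test (a check on complete simulated data gave 22.258 and 1.475 for both), so the sample size calculation is unaffected.

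**Cost.** SAP wording and slightly more analysis; no new data. The model assumes missing at random and does not restore power lost to missed visits. If missing patients do worse for unrecorded reasons, it can overstate the gain. In the simple case with no 6-month score, LOCF bias is -f × G_m and observed-pairs bias is f × (G_o - G_m), where G_o is the observed patients' gain. Carrying the pre-operative score is then closer to the truth only if G_m is below G_o/2. That is the case for keeping LOCF as a sensitivity analysis.

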## **6.3 DATA ANALYSES**

The following analyses will be performed:

1. Primary Endpoint – mean HHS score at 1 year
2. Second Endpoints – mean HHS score at other postop time points
3. Other Clinical Outcomes scores including EQ5D and UCLA
4. Comparison in clinical outcomes scores between preoperative and various postoperative time points
5. Survivorship with endpoint being revisions.

## **7. DATA COLLECTION, HANDLING AND RETENTION**

### **7.1 SOURCE DOCUMENTATION REQUIREMENTS**

Source documentation for this study will be maintained to document the treatment and study course of a subject and to substantiate the integrity of the data. Source documentation will include, but not be limited to, worksheets, hospital and/or clinic or office records documenting subject visits including study and other treatments or procedures, medical history and physical examination information, laboratory and special assessments results, pharmacy records, device accountability records, and medical consultations (as applicable).

### **7.2. CASE REPORT FORMS**

Data for this clinical trial will be collected and documented on the subject Case Report Forms (CRFs) provided, which may be in paper form or in an electronic form. Authorized study site personnel will complete CRFs only. CRFs must be reviewed and signed by the Investigator or his/her designees.

Since there is a potential for errors, inaccuracies, and misinterpretation in transcribing data onto the CRFs, the following documents must be available at all times for inspection and comparison to the CRFs by the study monitor where appropriate:

- data query forms
- originals and photocopies/certified copies of all relevant records and reports
- copies of test results

### **7.3. ELECTRONIC DATA ENTRY**

When using electronic trial data handling and/or remote electronic trial data systems, the sponsor should:

- Ensure and document that the electronic data processing system(s) conforms to the sponsor's established requirements for completeness, accuracy, reliability, and consistent intended performance (i.e. validation).
- Maintain SOPs for using these systems.
- Ensure that the systems are designed to permit data changes in such a way that the data changes are documented and that there is no deletion of entered data (i.e. maintain an audit trail, data trail, edit trail).
- Maintain a security system that prevents unauthorized access to the data.
- Maintain a list of the individuals who are authorized to make data changes (see 4.1.5 and 4.9.3).
- Maintain adequate backup of the data.
- Safeguard the blinding, if any (e.g. maintain the blinding during data entry and processing).

#### **7.4. STUDY DOCUMENT RETENTION**

Study documents should be retained for a season after the study is complete as required by local, state, national, or international health authorities.

### **8. DATA REPORTING**

#### **8.1 INTERIM REPORT**

An interim report will be provided after each follow-up period.

#### **8.2 FINAL REPORT**

Final report will be provided after 10 yr follow-up period.

### **9. MONITORING PLAN**

Biomet, as the sponsor of this study, may monitor the data collection to ensure that the investigation is being conducted consistent with the protocol. The following describes the monitoring activities, which may take place during the course of the study.

#### **9.1. FREQUENCY**

##### Pre-Investigational Visit/Conference:

Prior to initiation of the study, the study manager will provide the Investigator with all the necessary information to enable him to carry out his responsibilities. This prepares the site with an in-depth training on the protocol, case report forms, and data collection process for the length of the study. The study manager will also train the site on using the Biomet Joint Assist database.

A PROSPECTIVE SINGLE-CENTER STUDY ON E1 ACETABULAR LINER IN THA

### Monitoring of the Data

Monitoring of the data will occur at least annually, and as often as monthly. Times when this may be appropriate include:

- Monthly Invoicing
- Quarterly Review
- Annual Reports
- While performing data analysis for marketing material or publication.

## **9.2. SAMPLING PLAN**

All data will be monitored for completeness and accuracy on at least an annual basis.

## **9.3. MONITORING TASKS**

Biomet will continually monitor the progress of the clinical trial. These activities include:

- Tracking of patient enrollment
- Review of all electronic patient data forms received by Biomet for completeness
- Tracking of patients to ensure follow-ups are being completed at appropriate intervals
- Review of all adverse reactions
- Maintaining open communication with all investigational sites in order to ensure the quality of the clinical trial.
- In-House Audits as needed

Upon completion of any type of monitoring, the site is responsible for resolving all discrepancies found in a timely manner. These will be sent to the site with an audit report by the study manager. All discrepancies found within the Joint Assist database will be queried and sent directly to the site. Delays in resolving queries are to be avoided at all costs; this provides the study with the most accurate data, prevents delay in reporting procedures & publication, and safeguards in the event of an audit by the relative regulatory authority in the region.

## **9.4. STUDY CLOSE-OUT**

When a site has completed their data collection, a visit may be necessary by a Biomet monitor to ensure all data has been obtained. Data will be reviewed for completeness, and monitored to ensure that all discrepancies have been resolved.

# **10. ETHICAL AND REGULATORY REQUIREMENTS**

## **10.1. CODE OF CONDUCT**

The Investigator will ensure that the clinical study is conducted in accordance with

1. Protocol
2. Regulatory and IRB/EC requirements
3. ISO 14155, GCP

A PROSPECTIVE SINGLE-CENTER STUDY ON E1 ACETABULAR LINER IN THA

## **10.2. INSTITUTIONAL REVIEW/ETHICS COMMITTEE**

If required, the Investigator must obtain appropriate Independent Ethics Committee (IEC) approval before the study can be initiated. A copy of the written approval from the IEC and a copy of the approved informed consent form should be sent to the Sponsor.

Any changes to the protocol must be discussed and approved by the Sponsor in writing unless the change is made to assure the safety of the subject. In the non-emergent setting, after agreement on the changes has been reached, an amendment to the protocol will be provided by the Sponsor for submission to the IEC for review and approval prior to initiation of the change. Any change made emergently must be documented in the subject's medical record and reported to the Sponsor within the time period required by local SOPs and applicable regulations.

The Investigator must immediately forward to the IEC any written safety reports or updates from the Sponsor.

The Investigator must keep the IEC informed of the progress of the study as required by the IEC but at least annually.

## **10.3. INFORMED CONSENT**

Subjects (or the subject's legally authorized representative) will be provided with an informed consent and patient information sheet in order to give ample opportunity to review the consent and ask questions. The signed informed consent will be obtained before any study procedures begin. If the subject agrees to participate in the study, the subject/representative must sign the informed consent form. The witness and the Investigator must also sign the informed consent form. A copy of the informed consent form should be given to the subject/representative. All subjects who meet all of the entry criteria will be considered for inclusion in this trial. Any subject meeting any of the exclusion criteria will be excluded from the trial.

The informed consent form must be approved by the institution's IEC. Subjects will be informed of new information learned during the study, which may affect the subject's decision to continue participation in the study.

An Informed Consent Log will be completed to document the existence of the signed informed consent form. The log will contain: Subject ID, date informed consent form signed, and the version signed. The monitor will initial and date the log once the executed informed consent form has been reviewed. Signed informed consent forms (or copies) are to be maintained in the study file and must be available for verification by monitors or inspectors.

## **10.4. SUBJECT CONFIDENTIALITY**

To ensure study patients' privacy, all patients will be identified by unique identification numbers. All case report forms will only include patient IDs. It is the responsibility of the investigator to maintain a list of patient identification and Joint Assist.

Further the Joint Assist database is restricted, allowing a doctor to only view and enter data from his own patients. User authentication is required to view research data. The data is transmitted to a centralized database through a secured (SSL) channel on the Internet. Data in transit is in 128-bit encryption. The access to the centralized database is limited to those who are responsible for maintaining the database.

A PROSPECTIVE SINGLE-CENTER STUDY ON E1 ACETABULAR LINER IN THA

The Sponsor will maintain the confidentiality of the identity of subjects enrolled in the study and the information contained in their study records. The Sponsor will also instruct the study investigators in the importance of maintaining the confidentiality of study records. The records will be made available as required for review by governing regulatory agency such as FDA and a reviewing IEC/IRB, however to the extent possible, the subject's identity will not be disclosed.

## **11 RISK ANALYSIS**

The following warnings, precautions, and possible adverse effects associated with Total Hip Arthroplasty are as stated in the package insert for this device (attached).

### **WARNINGS**

Improper selection, placement, positioning, alignment and/or fixation of the implant components may result in unusual stress conditions which may lead to subsequent reduction in the service life of the prosthetic components. Malalignment of the components or inaccurate implantation can lead to excessive wear and/or failure of the implant or procedure. Inadequate preclosure cleaning (removal of surgical debris) can lead to excessive wear. Improper preoperative or intraoperative implant handling or damage (scratches, dents, etc.) can lead to crevice corrosion, fretting, fatigue fracture, and/or excessive wear. Do not modify implants. The surgeon is to be thoroughly familiar with the implants and instruments prior to performing surgery.

1. Acetabular screws are to be fully seated to assure stable fixation and to avoid interference with the acetabular liner component.
2. Prior to seating the liner into the shell component, all surgical debris (tissue fragments, etc.) must be removed from the interior of the shell component, as debris may inhibit the locking mechanism from engaging and securing the liner into the shell component.
3. Care is to be taken to assure complete support of all parts of the device embedded in bone cement to prevent stress concentrations, which may lead to failure of the procedure. Complete preclosure cleaning and removal of bone cement debris, metallic debris, and other surgical debris at the implant site is critical to minimize wear of the implant articular surfaces. Implant fracture due to cement failure has been reported.
4. In an instance where a liner engages the RingLoc™ locking ring and the liner is subsequently removed or replaced, the RingLoc™ locking ring should be replaced with a new ring.
5. Patient smoking may result in delayed healing, non-healing and/or compromised stability in or around the placement site.
6. The use of an elevated lip or offset polyethylene liner to correct for cup/liner malposition (cup abduction and/or anteversion) can lead to adverse loading of the unsupported portion of the polyethylene liner and increase the risk of liner fracture.

Biomet® joint replacement prostheses provide the surgeon with a means of reducing pain and restoring function for many patients. While these devices are generally successful in attaining these goals, they cannot be expected to withstand the activity levels and loads of normal, healthy bone, and joint tissue.

Accepted practices in postoperative care are important. Failure of the patient to follow postoperative care instructions involving rehabilitation can compromise the success of the procedure. The patient is to be advised of the limitation of the reconstruction and the need for protection of the implants from full load bearing until adequate fixation and healing have occurred. Excessive, unusual and/or awkward movement and/or activity, trauma, excessive weight gain, and obesity have been implicated with premature failure of certain implants by loosening, fracture, dislocation, subluxation and/or wear. Loosening of the implants can result in increased production of wear particles, as well as

A PROSPECTIVE SINGLE-CENTER STUDY ON E1 ACETABULAR LINER IN THA

accelerate damage to bone making successful revision surgery more difficult. The patient is to be made aware and warned of general surgical risks, possible adverse effects as listed, and to follow the instructions of the treating physician including follow-up visits.

Patient selection factors to be considered include: 1) need to obtain pain relief and improve function, 2) ability and willingness of the patient to follow instructions, including control of weight and activity level, 3) a good nutritional state of the patient, and 4) the patient must have reached full skeletal maturity.

